We are conducting this study as a pilot study. This pilot study's sample size is calculated based on the assumption that approximately 70% of the patients receive at least one dose of rescue opioid in the PACU. As this drug's efficacy in reducing the rescue opioids used in the PACU in this population is not studied previously, we plan to use a 50% rate reduction for calculating the sample size in this pilot study. According to our calculation estimate, we need to study 30 patients (alpha=0.05 and 1-Beta=0.85) in each group. The study will not be powered for secondary outcomes.

Descriptive statistics will be used to report all baseline demographic and clinical characteristics such as (age, gender, type of surgery, medications, ASA status, comorbidities). The primary endpoint amount of opioids used in the perioperative period will be compared using Wilcoxon rank-sum tests, and categorical variables such as adverse events and the number of patients requiring additional opioids will be analyzed using chi-square analysis or Fisher's exact tests. All the analysis will be two-tailed, and a p-value of <0.05 is considered statistically significant.

Data Management

All study data will be collected and entered into the computer database. Each subject will be assigned to a random number code, and the key linking the code and the subject identifier will be stored in a locked cabinet. The computer database will be password protected and will be kept on the HIPAA compliant Montefiore drive. The research manager is responsible for auditing the consistency of the data transcribed from the paper CRF to the computer. A protocol violation log will be maintained, and all protocol violations will be reported to the IRB and DSMB. The planned interim analysis (halfway through the recruitment) will be mainly focused on the additional dose of opioids in the PACU rather than the efficacy of the NMB reversal.

DSMB

The data safety monitoring board will be comprised of an anesthesiologist and a surgeon. All unanticipated serious adverse events will be reported to the DSMB. In the event of unanticipated serious adverse events, the continuation of the study will be at the discretion of DSMB and IRB. Periodic DSMB meetings will evaluate the occurrence of any study-related adverse events.

Human Safety

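### Thirty patients per group gives about 80% power (71% with Fisher's exact test) for a fall from 70% to 35%, not the stated 85%

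*Combined protocol and SAP*

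**What the plan says.** All the inputs are in the Statistical analysis section.

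- Rate without the study drug: "approximately 70% of the patients receive at least one dose of rescue opioid in the PACU".
- Effect: "we plan to use a 50% rate reduction for calculating the sample size in this pilot study".
- Result: "According to our calculation estimate, we need to study 30 patients (alpha=0.05 and 1-Beta=0.85) in each group".
- Sidedness, given in the next paragraph: "All the analysis will be two-tailed, and a p-value of <0.05 is considered statistically significant".
- Test for this kind of outcome: "the number of patients requiring additional opioids will be analyzed using chi-square analysis or Fisher's exact tests".

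The section names no formula or software and makes no allowance for dropout. It calls the study a pilot and says secondary outcomes are not powered.

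**The concern.** A reader who puts the plan's own rates, alpha and power into any common two-sided formula for two proportions gets more than 30 per group. This calculation is the plan's only justification of the sample size, so an ethics committee or safety board would take the 85% at face value.

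If true power is nearer 80% or 71%, a non-significant difference in rescue opioid use is weaker evidence of no effect than the plan implies. The choice between the two named tests also matters: it moves power by about 8 points, and the plan does not say which test the 85% refers to.

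**Working it through.** **Inputs.** p1 = 0.70 and two-sided alpha 0.05 (z = 1.960) are stated. Power 0.85 (z = 1.036) and 30 per group at 1:1 are stated. p2 = 0.70 × (1 − 0.50) = 0.35 is derived by reading the reduction as relative. Dropout is taken as zero.

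The difference is d = 0.35 and the mean rate is 0.525. The standard deviation terms are √(2 × 0.525 × 0.475) = 0.7062 under the null and √(0.70 × 0.30 + 0.35 × 0.65) = √0.4375 = 0.6614 under the alternative.

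**Trying to reproduce 30 per group at 85%, two-sided**

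- Pooled: n = (1.960 × 0.7062 + 1.036 × 0.6614)² / 0.35² = 2.0697² / 0.1225 = 34.97, so 35.
- Unpooled: n = 0.4375 × (1.960 + 1.036)² / 0.1225 = 32.07, so 33.
- Arcsine: h = 2·asin√0.70 − 2·asin√0.35 = 0.7162, and n = 2 × (2.996 / 0.7162)² = 35.01, so 36.
- Continuity-corrected: n = (34.97 / 4) × [1 + √(1 + 4 / (34.97 × 0.35))]² = 40.48, so 41.

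None gives 30.

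**Power at 30 per group, two-sided**

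- Pooled: (0.35 × √30 − 1.960 × 0.7062) / 0.6614 = (1.9170 − 1.3842) / 0.6614 = 0.806, so 79.0%.
- Unpooled: 1.9170 / 0.6614 − 1.960 = 0.938, so 82.6%.
- Arcsine: 0.7162 × √15 − 1.960 = 0.814, so 79.2%.
- Exact, summing binomial probabilities over all 31 × 31 possible outcomes: uncorrected chi-square 79.8%, Fisher 71.4%, Yates-corrected chi-square 71.4%.

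The last line matters most, because it gives the power of the tests the plan names. The corresponding beta is 0.20 (uncorrected chi-square) or 0.29 (Fisher or Yates), against a stated 0.15.

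**Where a figure near 30 could come from**

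| Change to the stated inputs | n per group |
|---|---|
| Two-sided, 80% power, pooled | 30.75, so 31 |
| One-sided, 85% power, pooled | 27.85, so 28 |
| One-sided, 80% power, continuity-corrected | 29.54, so 30 |
| Two-sided, 85% power, pooled, treated rate 32% | 30 |
| Two-sided, 85% power, pooled, reduction read as 50 points (70% to 20%) | 17 |

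Each of the first four departs from something the plan states: the power, the sidedness, both, or the effect size. A treated rate of 32% is a relative reduction of (0.70 − 0.32) / 0.70 = 54%, not 50%. Reading the reduction as percentage points does not lead to 30 either; it would give 98.7% power at 30.

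**What 85% would take.** Fisher's test has exact power of 84.3% at 39 per group and 85.9% at 40. Exact power of the uncorrected chi-square rises and falls with n: 85.6% at 33, 82.8% at 34, 83.5% at 35, 85.1% at 36, and above 85% at every size checked from 36 to 45.

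**The case against.** The strongest reply is that little turns on the gap. This is a pilot, the effect is a planning choice with no prior data, and the 70% is approximate. With the uncorrected chi-square the shortfall is about 5 points. A baseline of 75% with the same halving gives 85.2% at 30 per group (pooled formula). That is true, but a baseline of 65% gives 72.3%, so the uncertainty runs both ways. Pilot status could justify 30 on feasibility, but it does not make a stated power correct.

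Second, the sample-size sentence does not say whether alpha is one- or two-sided. One-sided, the pooled formula needs 28 and gives 87.3% at 30, so the error may be an undeclared one-sided input. That is plausible as a cause, but it conflicts with the statement "All the analysis will be two-tailed". The power of the planned analysis is still the two-sided one.

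Third, Fisher's test may not be the one used. Under the planning rates the expected cell counts are 30 × 0.525 = 15.75 and 30 × 0.475 = 14.25, so the usual small-count reason for it does not arise. This stands: about 80% is the main figure, and 71% applies only if Fisher or the Yates correction is used. The plan leaves both tests open.

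Fourth, the calculation concerns a yes/no rescue outcome, whereas the primary endpoint is total perioperative opioid dose compared by the Wilcoxon rank-sum test. This also stands. None of 85%, 80% or 71% is the power of the primary analysis, so the consequence described here is limited to the rescue-opioid comparison. That mismatch is a separate matter, and the 85% is wrong even for the outcome it was calculated on.

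**Conclusion.** The concern holds. On the plan's own inputs, 30 per group does not give 85% power by any two-sided method tried; the most favourable approximation gives 82.6%. For the named tests the power is 79.8% (uncorrected chi-square) or 71.4% (Fisher), a shortfall of about 5 or 14 points. In patients, the pooled formula is short by 5 per group (35 against 30), and Fisher's test by 10 (40 against 30).

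This assumes that the reduction is relative, that the groups are equal, that alpha is two-sided as the analysis paragraph says, and that nobody is lost. Any loss would lower power further.

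**What to change.** Replace the sample-size sentence with one that matches the design, for example: *With 30 patients per group, the uncorrected chi-square test has about 80% power (Fisher's exact test about 71%) at two-sided alpha 0.05 to detect a fall from 70% to 35% in the proportion of patients receiving rescue opioid in the PACU; this is not the power for the primary endpoint.* Name the single test that will be used and keep only its figure. The cost is one sentence and a less favourable stated power; enrolment and the conduct of the study do not change.

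If the sponsor wants to keep 85%, the design needs 36 per group for the uncorrected chi-square or 40 for Fisher's test. Alternatively, 60 comparison charts against 30 treated patients would give about 88% (Fisher) to 90% (uncorrected chi-square), at the cost of 30 more chart reviews. That depends on enough eligible comparison patients having surgery between the first and last treated patient, which the documents do not show, so it should be checked before it is adopted.

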The safety and efficacy of sufentanil have been demonstrated in different types of surgeries. After hip or knee arthroplasty, patients who received sublingual sufentanil reported lesser postoperative pain compared to placebo.¹⁴ Similar results were reported by patients who had undergone open abdominal surgery.¹⁵ Additionally, in one of the recent publications, the use of sublingual sufentanil in the preoperative period resulted in reduced opioid usage in the post-operative period and shorter time in the postoperative anesthesia care unit.¹⁶

In this case, series, we are testing the hypothesis that sublingual sufentanil (Dsuvia) will improve postoperative pain management in the PACU in ambulatory surgery patients taking Suboxone.

Primary Endpoint – We will evaluate the total amount of morphine equivalence (MME) in the perioperative period (defined as combined total opioid used intra-op and in the PACU).

Secondary Endpoint(s) – We will evaluate the time to fit to discharge from the PACU, the need for additional opioids and time to take the first additional opioid within 24 hours after being discharged from the hospital, and finally, the adverse events in the intraoperative period , PACU and in the 24 hours after being discharged from the PACU (i.e., nausea, vomiting, itching, hypotension, dizziness.)

Methods

Study Design:

Prospective case series study.

Inclusion criteria

- Age range 18-100 years
- Currently taking Suboxone
- ASA physical score 1-3
- Able to provide a signed informed consent
- General anesthesia (either endotracheal intubation or laryngeal mask airway) or **MAC** (**monitored anesthesia care**) without the use of regional anesthesia

Exclusion criteria

- Known allergic reactions to Dsuvia and its excipients
- Severe respiratory illness including exacerbation of asthma attack
- Significant intraoperative hemodynamic instability
- Use of Regional anesthesia techniques

Informed Consent

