According to the Montefiore standard of care, to prepare patients for surgery, the perioperative team contact patients within 1-3 days before the surgery. During this phone call, patients are given all the instructions regarding the surgical preparation, and the operative team makes sure all the needed medical records are in place. During this phone call, patients will be specifically asked about suboxone use, and an email will be sent to the research team to inform the details of the suboxone patients. The research team will screen the patients and those patients fulfilling the inclusion-exclusion criteria will be called on the day before surgery for their interest in participating in a research study. Interested patients will be provided with the study details, and all their questions will be answered. The signing of the consents will take place on the day of the surgery, an investigator associated with the study will be responsible for obtaining the informed consents.

In terms of surgery and anesthesia, the routine standard of care practiced in our hospital will be maintained for all the subjects enrolled in the study. During the study period, all the intraoperative and postoperative patient pain management guidelines will be standardized. According to the standard of practice in our institution, induction of anesthesia will take place. After induction of anesthesia, instead of intra-op and post-op Fentanyl 50mcg as needed, the patients will receive sublingual sufentanil (Dsuvia) intra-op and post-op. Detailed sublingual sufentanil is described in the next paragraph. Patients will be discharged home based on the discharge criteria followed at our institution. One of the research associates will call the patient 24 hours after discharge from the PACU to collect the information regarding their post-discharge opioid use, current pain score, adverse events, and information regarding the ED visits.

Study Objective Assessments

A research associate will be collecting the data prospectively and from the medical records. All the assessments will be coordinated with the standard of care administered at our hospital.

Study Medication and Storage

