The sponsor of the study is responsible for providing the study medication. The patient or the insurance will not be billed for the study medication. Study medication will be stored in the research pharmacy at Hutch. All appropriate storage instructions will be followed, and the pharmacist will be responsible for the drug audit. On the day of surgery for an enrolled subject, research personnel will retrieve medication from the pharmacy and deliver it to the physician for administration to subjects.

Sublingual sufentanil (Dsuvia) Study Protocol Pain Medications:

Pre-op:

Acetaminophen 975mg PO

Intra-op for induction (doses as per standard):

IV Midazolam

IV Fentanyl

IV Lidocaine

IV Propofol

After induction and before incision

Ketamine .35-.5 mg/kg IV

Dsuvia 30mcg SL (1st dose)

Postop:

If pain < or = 4/10,

Give no additional medications

If pain > 4/10

give Dsuvia 30mcg SL (2nd dose)

if 30 minutes after Dsuvia 2nd dose & pain is >4/10

give Ibuprofen 800mg IV

if 60 minutes after Dsuvia 2nd dose & pain is >7/10

give hydromorphone 0.4 mg IV

Interim Analysis

We are planning to conduct an interim analysis to evaluate the use of a single dose of Dsuvia in the intraoperative period. For this purpose, if 8 of the first 15 patients require a second dose of Dsuvia in the PACU, then the protocol will be changed to give the 2nd dose of Dsuvia in the OR at 15 minutes (or more) before extubating (and more than 1 hour since the 1st dose). The rest of the protocol will stay the same.

Comparison group

The comparison group in this study will be randomly selected from a cohort of the patients satisfying inclusion and exclusion criteria. The time frame for the comparison group will be the first Dsuvia patient to the last Dsuvia patient. For the comparison group, all the data points will be collected retrospectively. For comparison, group data points after the discharge from the hospital will not be collected. We are requesting a waiver of consent and HIPAA authorization for the comparison group as this will be

conducted retrospectively. A waiver will be needed because subjects may not be possible due to reasons such as relocation, wrong contract information given, or are no longer being seen at our institution.

Statistical analysis

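### Comparators are sampled rather than randomised, their co-analgesics are not stated and the MME test is unadjusted, so an MME difference cannot be credited to Dsuvia alone

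*Combined protocol and SAP*

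**What the plan says.** All references are to the combined protocol and SAP.

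- **Who is in each group.** Under Informed Consent, "those patients fulfilling the inclusion-exclusion criteria will be called on the day before surgery for their interest in participating in a research study", and those who are interested sign consent on the day of surgery. Under Comparison group, "The comparison group in this study will be randomly selected from a cohort of the patients satisfying inclusion and exclusion criteria". Comparators come from the same calendar period, from records, under a requested consent waiver.
- **Anaesthesia.** The inclusion criteria admit both GA and MAC.
- **Treatment.** The Informed Consent section says that "instead of intra-op and post-op Fentanyl 50mcg as needed, the patients will receive sublingual sufentanil (Dsuvia) intra-op and post-op". It also says that routine care is maintained and that "all the intraoperative and postoperative patient pain management guidelines will be standardized". The medication list is headed as the Dsuvia study protocol. It contains acetaminophen before surgery, ketamine before incision, and ibuprofen as a PACU step. There is no corresponding list for comparators.
- **Endpoint and test.** Primary MME is "defined as combined total opioid used intra-op and in the PACU". Under Statistical analysis, "The primary endpoint amount of opioids used in the perioperative period will be compared using Wilcoxon rank-sum tests", two-sided at 0.05. For baseline variables, including type of surgery, medications and ASA status, "Descriptive statistics will be used to report all baseline demographic and clinical characteristics".
- **Secondary endpoints.** Adverse events and additional opioids run to 24 hours after discharge. No post-discharge data are collected for comparators. The chi-square and Fisher tests are given no time window.

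**The concern.** The Introduction's hypothesis attributes better PACU pain management to Dsuvia itself, and the plan tests MME at the 5% level. The design cannot isolate that effect, for two reasons.

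First, patients who volunteer and a sample of all eligible patients may differ in anaesthesia type, surgery or other features that drive opioid use, and nothing in the analysis allows for this. Second, if comparators do not receive ketamine and acetaminophen as the Dsuvia patients do, the contrast is between two packages of care. Either could produce an MME difference with no Dsuvia effect, or hide a real one.

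A smaller matter concerns the secondary endpoints: what happens after discharge is observed in one group only, so it cannot be compared between groups.

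**Working it through.** **1. The plan's own figure.** The only computed figure is 30 per group. It assumes that "approximately 70% of the patients receive at least one dose of rescue opioid in the PACU", and a halving of that rate: 0.70 × 0.5 = 0.35. The pooled two-sided formula, n = [1.960·√(2·0.525·0.475) + 1.036·√(0.21 + 0.2275)]² / 0.35², gives (1.384 + 0.686)² / 0.1225 = 35. The one-sided version gives 28. So 30 is not reproduced under the stated two-tailed test. That is a separate issue; 30 per group is taken below as planned.

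**2. The passages side by side.**

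| Feature | Dsuvia group | Comparators |
|---|---|---|
| Entry | phoned, interested, consenting | random sample of eligible records |
| Opioid | Dsuvia in place of as-needed fentanyl | as-needed fentanyl (implied) |
| Acetaminophen, ketamine | listed | not stated |
| Ibuprofen | listed, after the second Dsuvia dose | not stated |
| GA or MAC | either | either |
| MME, intra-op plus PACU | available | available |
| 24 h after discharge | collected | not collected |

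In the Dsuvia group, ibuprofen comes only after the second tablet, so it can affect only the later hydromorphone step. Ketamine and acetaminophen precede all PACU dosing and could affect more of the total.

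**3. What cannot be computed.** The documents give no MME mean or SD, no MAC share, no co-analgesic use in comparators and no MME conversion for the tablet. The conversion matters. Every Dsuvia patient receives a tablet before incision that counts in MME, and comparators do not. If it converts to less than the as-needed opioid it replaces, Dsuvia MME falls; if to more, it rises. The direction of a co-analgesic bias in total MME is therefore open, and no rejection rate is offered for it.

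**4. Illustration for GA/MAC mix.** Everything here except 30 per group and two-sided 5% is assumed: no Dsuvia effect, lognormal MME with log-scale SD 0.5, 0.7 or 0.9, and MAC halving use. Splits are the MAC share in one group against the other.

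| MAC split | Unadjusted Wilcoxon, SD 0.5 / 0.7 / 0.9 | Same, exact counts |
|---|---|---|
| 60/40 | 14.4% / 9.9% / 8.8% | 6–9% (18 vs 12 of 30) |
| 70/30 | 43.4% / 27.7% / 18.4% | 16–42% (21 vs 9 of 30) |

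In the middle column each patient's anaesthesia type is drawn with the stated probability; in the last the counts are fixed. Together they give about 6–15% and 16–43%.

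Hand check of the middle column at SD 0.5:
- 60/40: log shift 0.2 × ln 2 = 0.139; total SD √(0.25 + 0.24 × 0.480) = 0.604; ratio 0.23 SD.
- 70/30: log shift 0.4 × ln 2 = 0.277; total SD √(0.25 + 0.21 × 0.480) = 0.592; ratio 0.47 SD.
- For a normal outcome at 30 per group, the Wilcoxon test rejects in about 15% at 0.25 SD and 45% at 0.5 SD, in line with 14.4% and 43.4%.

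**5. Stratified test.** Van Elteren sums w·[R − m(N+1)/2] over strata with w = 1/(N+1), where R is the Dsuvia rank sum, m the Dsuvia count and N the stratum total. In the randomly drawn cases above it rejects in 4.5–5.4%. This follows largely by construction, because MAC is the only confounder simulated.

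**6. Power cost of two strata** (lognormal, assumed 40% MME cut; SD 0.5 / 0.7 / 0.9):

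| MAC | Unadjusted | Stratified | Change, points |
|---|---|---|---|
| 60/40, no effect on MME | 96.5 / 77.2 / 55.6% | 95.2 / 74.1 / 51.9% | −1.3 / −3.1 / −3.7 |
| 50/50, no effect on MME | 96.6 / 77.2 / 55.9% | 96.1 / 75.4 / 54.3% | −0.5 / −1.8 / −1.6 |
| 50/50, halves MME | 86.9 / 67.7 / 49.9% | 96.1 / 75.8 / 54.1% | +9.2 / +8.1 / +4.2 |

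**The case against.** The documents call this a case series and a pilot and never claim random allocation. Comparators are concurrent and meet the same criteria. Guidelines are to be standardised during the same period, and the only named change is fentanyl to Dsuvia, so shared background care is a fair reading. Medications and type of surgery will at least be described. GA/MAC is one confounder among several: the documents give no MAC share or effect, and the regimen's references to induction and extubation suit GA. If MAC were 50% in both source groups, a chance gap of 40 points or more would have a probability of about 0.3%, so 70/30 needs systematic selection, of which there is no evidence.

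Much of this stands. Concurrency limits calendar drift, the 70/30 case is a strong assumption, and shared co-analgesics are possible. It does not remove the point. The standardisation sentence names no comparator co-analgesic and follows one about enrolled subjects. Concurrency does nothing about volunteer selection. The pilot label sits beside a hypothesis about Dsuvia tested at p<0.05.

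A reader might infer three stronger things that the documents do not support:
- That the groups do differ in case mix or co-analgesics. They may; nothing shows that they do.
- That the MME comparison is biased towards Dsuvia by a known amount. Neither size nor direction can be derived.
- That the adverse-event test is biased against Dsuvia. That needs uncollected comparator events to be counted as none, which the plan does not say.

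**Conclusion.** The point holds as a limit on inference, and the plan should be changed. Comparators are not randomly allocated, the primary test is unadjusted, and shared co-analgesics are possible but not established. A significant MME difference would support at most the Dsuvia-based regimen against usual care in these patients, not Dsuvia alone as hypothesised. MME itself is observable in both groups; only the post-discharge secondary endpoints lack a comparator.

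The rejection rates of 6–15% and 16–43% show what an anaesthesia imbalance could do. They rest on an assumed lognormal shape, assumed SDs, an assumed halving of use under MAC and assumed splits, and are not estimates for this trial. The conclusion does not depend on them.

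**What to change.** 1. **Prespecify a van Elteren (stratified Wilcoxon) comparison of MME by GA versus MAC, beside the unadjusted test.** The cost is SAP wording and up to about 4 points of power if MAC is split 60/40 but does not affect MME; where MAC matters, power rises. If all patients have GA, the two tests coincide. Keep to two strata: with 30 per group, six lose 3–9 points in the same lognormal cases. Other confounding, such as type of surgery, remains.
2. **Abstract ketamine, acetaminophen and NSAID use from the comparator charts already under review, and report it by group.** Word the conclusion as the Dsuvia-based regimen versus usual care in a non-randomised comparison, unless that use is balanced. Stratifying by GA/MAC does not remove a co-analgesic effect, and no adjustment can separate Dsuvia from drugs that all treated patients receive and few comparators do. The cost is a few chart fields and a narrower claim.
3. **Limit between-group tests of adverse events and additional opioids to the intraoperative and PACU window.** Report the 24-hour data descriptively, for Dsuvia patients only. The cost is a shorter comparative safety window.

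All three should be written in before outcome data are examined, so that neither the adjustment nor the window is chosen on the results.
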